Appendix 3. France Country-Specific Requirement

This appendix applies to study sites located in France.

Per France regulations, a France-specific protocol appendix is to be included in the final approved protocol to capture some operational items not included in the mandatory contract format for France (ie, French “Contract Unique”), which Pfizer includes in standard contract language for other countries. The following items included do not impact the conduct of the trial, the safety or integrity of the participant, or use of their data:

1. GCP Training

Prior to enrollment of any participants, the investigator and any sub-investigators will complete the Pfizer-provided Good Clinical Practice training course (“Pfizer GCP Training”) or training deemed equivalent by Pfizer. Any investigators who later join the study will complete the Pfizer GCP Training or equivalent before performing study-related duties. For studies of applicable duration, the investigator and sub-investigators will complete Pfizer GCP Training or equivalent every three years during the term of the study, or more often if there are significant changes to the ICH GCP guidelines or course materials.

2. SUSARs

Pursuant to a sponsor’s safety reporting obligations under 21 Code of Federal Regulations (CFR) 312.32(c)(1), Pfizer will report to the investigator all Serious Unexpected Suspected Adverse Reactions (“SUSARs”). The investigator will receive and review SUSAR reports and report SUSARs to the responsible IRB/IEC according to institution’s guidelines.

Institution will retain SUSAR reports consistent with [Section 11.2](#) of the Protocol.

Appendix 4. Turkey Country-Specific Requirement

Protocol Title

The original C0371004 study (hemophilia B cohort) was approved as an observational study in Turkey, as there was no intervention in the SoC factor replacement prophylaxis treatment and all the treatment decisions are taken by the investigators. This design is aligned with the requirements defined in the local Turkish regulatory “Guideline for Observational Drug Studies (13 November 2015).”⁷ The study title was changed with protocol amendment 3 to include hemophilia A cohort and reference to subsequent Phase 3 studies, in order to clarify that the two lead-in study cohorts will participate in separate Phase 3 studies. Subsequently, on 11 November 2019, the Turkish MoH requested that the text regarding subsequent Phase 3 studies be deleted from the protocol title, as it is out of the scope of the objectives for the current study as defined in the regulatory guideline.

Protocol amendment 4, which reflects protocol changes specific to Turkey, removes the following text from the protocol title: “*Prior to the Respective Therapeutic Phase 3 Gene Therapy Studies.*”

The protocol title for use specific to Turkey will be as follows:

- “*An open-label, non-investigational product, multi-center, lead-in study to evaluate prospective efficacy and selected safety data of current Factor IX (FIX) or Factor VIII (FVIII) prophylaxis replacement therapy in the usual care setting of moderately severe to severe adult hemophilia B participants (FIX:C≤2%) who are negative for neutralizing antibodies to adeno-associated virus vector-Spark100 (BENEGENE-1) and moderately severe to severe hemophilia A adult participants (FVIII:C≤1%) who are negative for neutralizing antibodies to adeno-associated virus vector 6 (AAV6).*”

Comprehensive study documents which apply to all countries, including the clinical study report and any protocol amendments, will include a description of the protocol title change for Turkey, but these documents will reflect the original study title. Shorter documents which apply to all countries, such as administrative letters, will not reflect the title change for Turkey but will reflect the original study title. Participant facing materials in Turkey will use the protocol title specific to Turkey.

Document Approval Record

Document Name: C0371004 Protocol Amendment 8_31March2023

Document Title: C0371004 Protocol Amendment 8_31March2023

Signed By:	Date(GMT)	Signing Capacity

1. VERSION HISTORY

This statistical analysis plan (SAP) for study C0371004 is based on the protocol updates as described in the below table.

Version/ Date	Associated Protocol Amendment	Rationale	Specific Changes
5.0/19 Sep 2024	8.0/31MAR2023	Protocol amendments, text accuracy, and statistical summary completeness and accuracy	
Increased sample size for both cohorts to align with protocol amendments (Section 2.2).
 
Updated text describing the algorithm used to count bleeds for ABR (Section 3.1).
 
Updated text for nAb status endpoint for accuracy and removed the analysis combining both hemophilia A and B cohorts (Sections 3.3, 4.2, 5, 6.3.1).
 
Removed text saying PA#5 and the corresponding analyses were only applicable to hemophilia B cohort.
 
Updated Figure 2 and references to it to align with this change (Sections 4, 4.2, 4.4, 4.5, 6.1.1, 6.2.2).
 
Added summary of prospective data for PA#5 analysis set (Section 6.1.1).
 
Added clarifying text on reason for exclusion from efficacy analysis set (Section 4.2).
 
Updated definition of safety analysis set (Section 4.3).
 
Updated the name of the region 'Asia Pacific' to 'Asia' (Section 6.3.1).
 
Added summary of follow-up duration (Section 6.5.2).

4.0/25 Mar 2021	5.0/01OCT2020	Summary method update	
 1. Added algorithms for defining treated bleeds (Section 3.1). 2. Updated summary method for ABR and AIR. 3. Added Section 6.7 COVID related outputs.
3.0/14Jan2021	5.0/01OCT2020	Protocol amendment	This SAP is updated to align with the protocol amendment 5 which increased sample size for participants with hemophilia B to support an additional cohort planned for the

			subsequent Phase 3 registration study.
2.0/17DEC2019	3.0/27JUN2019	Protocol amendment	This SAP is updated to align with the protocol amendment which includes an additional cohort (hemophilia A participants) as part of the 6-month lead-in study, to accelerate the initiation of the hemophilia A gene therapy phase 3 study.
1.0/20JUN2018	Original /23MAR2018	NA	NA

2. INTRODUCTION

This SAP provides the detailed methodology for summary and statistical analyses of the data collected in study C0371004. This document may modify the plans outlined in the protocol; however, any major modifications of the primary endpoint definition or its analysis will also be reflected in a protocol amendment.

Any deviations from this analysis plan will be described in the Clinical Study Report.

2.1. Study Objectives

Primary Objective(s):	Efficacy Endpoint(s):

 To establish prospective efficacy data of: 
 Factor IX (FIX) prophylaxis replacement therapy in the usual care setting of hemophilia B participants, who are negative for neutralizing antibody (nAb) to adeno-associated virus vector (AAV)-Spark100. Factor VIII (FVIII) prophylaxis replacement therapy in the usual care setting of hemophilia A participants, who are negative for nAb to AAV6 	
Efficacy Endpoint(s):
 
Primary Endpoint
 
 Annualized bleeding rate (ABR) in hemophilia B participants. Annualized bleeding rate (ABR) in hemophilia A participants. 
Secondary Endpoint
 
 Annualized number of infusions (AIR) in hemophilia B participants. Annualized number of infusions (AIR) in hemophilia A participants. 
Other Secondary Endpoints
 
 Dose and total factor consumption in hemophilia B participants. Dose and total factor consumption in hemophilia A participants. Number of bleeding events (spontaneous and/or traumatic) in hemophilia B participants.

	
 Number of bleeding events (spontaneous and/or traumatic) in hemophilia A participants.
Secondary Objective(s):	Safety Endpoint(s):

 Evaluate safety (serious adverse events and medically important events of FIX or FVIII inhibitor, thrombotic and factor hypersensitivity reactions) of FIX replacement therapy in hemophilia B participants and FVIII replacement therapy in hemophilia A participants. 	
 Incidence of serious adverse events in hemophilia B participants. Incidence of serious adverse events in hemophilia A participants. Events of special interest in hemophilia B participants: 
 FIX inhibitor; Thrombotic events; Factor hypersensitivity events. Events of special interest in hemophilia A participants: 
 FVIII inhibitor; Thrombotic events; Factor hypersensitivity events.
Exploratory Objective(s):	Exploratory Endpoint(s):

 Measure the frequency of nAb against AAV-Spark100 and AAV6 in the respective population assessed (hemophilia B or hemophilia A participants). 	
 The frequency and percentage of nAb status to AAV-Spark100 and AAV6 (positive, negative).

[figure not shown]
2.2. Study Design

The C0371004 study will be conducted as an open-label, non-investigational product, prospective, multi-center, lead-in study to assess efficacy and selected safety data of current factor (FIX) or factor VIII (FVIII) prophylaxis replacement therapy in the usual care setting of moderately severe to severe adult hemophilia B participants (FIX:C \leq 2%) who are negative for nAb to AAV-Spark100, and moderately severe to severe adult hemophilia A participants (FVIII:C \leq 1%) who are negative for nAb to AAV6, prior to the subsequent Phase 3 gene therapy study C0371002 (hemophilia B) and C3731003 (hemophilia A) respectively. The study consists of two phases: the screening phase will include laboratory blood draw to determine nAb to either AAV-Spark100 or AAV6 in each respective group of participants (hemophilia B cohort and hemophilia A cohort) and the second phase will be the data collection phase for those hemophilia B participants who are below the established threshold for nAb to AAV-Spark100 and those hemophilia A participants who are below the established threshold for nAb to AAV6. The nAb-negative participants will be contacted to schedule a baseline visit to confirm eligibility, to issue their electronic infusion diary and continue on with the data collection phase. The baseline visit is defined as Day 1, which is the start of the prospective data collection phase. The duration of follow-up for participants

in this study (C0371004) will be at least 6 months until the respective thresholds of dosed participants are met. Subsequent to reaching the threshold in the dosing study, the duration of follow-up for participants recruited into this study (C0371004) will be dictated by the timing of their enrollment into the subsequent treatment protocol and may be less than 6 months. It is anticipated most participants will be followed for at least 6 months during the data collection phase, which is designed to provide prospective efficacy and selected safety data of FIX prophylaxis replacement therapy or FVIII prophylaxis replacement therapy in the usual care setting for hemophilia B and hemophilia A participants respectively. The participants of this lead-in study could subsequently participate in a dosing study of hemophilia B gene therapy of PF-06838435 or hemophilia A gene therapy of PF-07055480, if they properly complete this study and meet the inclusion/exclusion criteria for the subsequent trials.

The primary efficacy endpoint for C0371004 study will be annualized bleeding rate (ABR). The secondary efficacy endpoint will be annualized infusion rate (AIR). Additional secondary efficacy endpoints are factor consumption (dose and total) and number of bleeding events (spontaneous and/or traumatic). Primary and secondary endpoints will be evaluated separately in the respective hemophilia B and hemophilia A populations. The exploratory endpoint is the frequency of each nAb status (positive, negative) to AAV-Spark100 and to AAV6 in each of the respective populations assessed.

Figure 1. Study Schematic

Hemophilia B:

The sample size for this hemophilia B cohort is based on the number of evaluable participants needed for the subsequent Phase 3 registration study C0371002, ie, N=80 to be enrolled and treated in C0371002; it is anticipated that 60 participants will have at least 6 months of follow-up data from this study [C0371004]; for the remaining participants, the duration of follow-up data from this study [C0371004] may vary depending on the timing of their enrollment into the subsequent treatment protocol [C0371002]). It is expected that the

attrition rate between this study and C0371002 will be approximately 20%. Additionally, it is anticipated that approximately 10% of participants in C0371004 will not complete the study. Therefore, it is estimated that 111 participants will need to be enrolled to allow approximately 100 participants to complete study C0371004 and be eligible for enrollment into C0371002.

Hemophilia A:

The minimum sample size for this hemophilia A cohort is based on the minimum number of evaluable participants needed for the primary analysis of the subsequent Phase 3 registration study C3731003 (ie, at least N=50 with at least 6 months of follow-up data from this study [C0371004] to reach the primary analysis time point in C3731003). It was initially anticipated that approximately 20% of participants in C0371004 would not enter the C3731003 study. However, the attrition rate was higher than expected following the temporary pause in the subsequent Phase 3 study (C3731003). Therefore, it is now estimated that approximately 95 participants will need to be enrolled in this cohort to allow approximately 70 participants to be enrolled into C3731003 to provide the minimum sample size required for C3731003. A sufficient number of participants will be screened in this study [C0371004] in order to enroll approximately 95 participants.

Participants withdrawn from the study or the subsequent treatment study may be replaced, at the discretion of the investigator and Sponsor (Pfizer, Inc).

3. ENDPOINTS AND BASELINE VARIABLES: DEFINITIONS AND CONVENTIONS

3.1. Primary Endpoint(s)

The primary endpoint is ABR (treated and total). A bleeding episode is defined in Protocol Appendix 2.

If a bleed is treated with FIX infusion (for Hemophilia B) or FVIII infusion (for Hemophilia A) (according to Bleeding eDiary or Bleeding CRF) within 72 hours post the start of bleeding (by comparing date/time of bleeding to date/time of infusion in Infusion eDiary or Infusion CRF), regardless of the type of treatment (preventive, prophylaxis or rescue medication), it will be considered as a treated bleed. If a bleed is not treated with FIX/FVIII infusion according to the Bleeding eDiary or the Bleeding CRF, the bleed will not be considered as a treated bleed but considered as an untreated bleed.

If there are multiple concurrent bleeds (spontaneous or traumatic) on the same date AND time but in different locations in a participant, they will be recorded as one bleed for that participant. If concurrent bleeds occurred on the same day but at different times and different locations, they will be counted as separate bleeds. Only new bleeds (as defined in Protocol Appendix 2) will be counted toward the number of bleeds for ABR calculation.

For untreated bleed, every occurrence will be counted as a separate bleed.

The ABR per participant based on prospectively collected bleeds will be calculated as:

The number of bleeds (all treated bleeding episodes including spontaneous and traumatic) x 365.25 days/number of days during the observation time period while the participant received prophylaxis factor replacement therapy in the usual care setting from baseline visit (Day 1) to end of study (date of study completion or discontinuation, whichever is earlier).

Number of bleeds (treated bleeds and all bleeds, respectively) and infusions within the last 12 months will be collected at the screening visit using hemophilia history CRF for all participants enrolled under Protocol Amendment 5 (01 Oct 2020) or under a subsequent protocol amendment. Thus the retrospectively collected ABR per participant will be equal to number of bleeds in the past 12 months collected in the Hemophilia History form.

Participants enrolled in hemophilia A cohort or hemophilia B cohort prior to Protocol Amendment 5 will not have the CRF retrospectively filled out.

ABR combining retrospective and prospective data will be calculated as:

$$\frac{(\text{Number of bleeds from baseline visit (Day 1) to end of study} + \text{Number of bleeds collected in Hemophilia History form})}{(\text{Number of days from baseline visit (Day 1) to end of study} + 365.25)/365.25}$$

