The aim of this study is to assess prospective efficacy of FIX or FVIII prophylaxis replacement therapy in the usual care setting of moderately severe to severe hemophilia B or hemophilia A participants, respectively, whose nAb to AAV-Spark100 (hemophilia B participants) and nAb to AAV6 (hemophilia A participants) are below the established thresholds (negative). The FIX and FVIII prophylaxis efficacy data obtained in this study will serve as the control for comparison with post gene therapy efficacy for those participants that subsequently enroll into and are treated in the respective subsequent Phase 3 gene therapy dosing studies (C0371002 hemophilia B and C3731003 hemophilia A).

There is no single reference safety document (SRSD) for this protocol with each product supported by their respective approved product label.

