9. DATA ANALYSIS/STATISTICAL METHODS

Detailed methodology for summary and statistical analyses of the data collected in this study is outlined here and further detailed in a statistical analysis plan (SAP), which will be maintained by the sponsor. The SAP may modify what is outlined in the protocol where appropriate; however, any major modifications of the primary endpoint definitions or their analyses will also be reflected in a protocol amendment.

All data analyses will be performed separately for each population (hemophilia A and hemophilia B). There will be no joint analysis done that includes both populations together outside of the exploratory endpoint of neutralizing antibody positivity rates.

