Appendix 2. Bleed and Factor Replacement Regimen Definitions^{1,2,3}

Definition of a Bleed (for analysis purposes)

Treated Bleed: An event necessitating administration of coagulation factor within 72 hours of signs or symptoms of bleeding (protocol definition, unless specifically referring to untreated bleed).

Untreated Bleed: A bleeding event not necessitating administration of coagulation factor within 72 hours of signs or symptoms of bleeding.

New Treated Bleed: A treated bleed occurring >72 hours after stopping treatment from the original bleed for which treatment was initiated or a treated bleed occurring at a different site from the original bleed regardless of the time from last injection.

New Untreated Bleed: An untreated bleed occurring >72 hours after the previous untreated bleed at the same site or occurring >72 hours after stopping treatment from the original bleed for which treatment was initiated, or an untreated bleed occurring at a different site from the original bleed regardless of the time from last bleed or last injection.

Definition of a Bleed Location

Target Joint: Defined as a major joint (eg, hip, elbow, wrist, shoulder, knee, and ankle) into which repeated bleeds occur (three or more spontaneous bleeds into a single joint within a consecutive 6-month period). A target joint is considered resolved when there are ≤ 2 bleeds into the joint within a 12-month period.

Joint Bleed: A bleeding episode characterized by rapid loss of range of motion as compared with baseline that is associated with any combination of the following: pain or an unusual sensation in the joint, palpable swelling, and warmth of the skin over the joint.

Muscle Bleed: An episode of bleeding into a muscle, determined clinically and/or by imaging studies, generally associated with pain and/or swelling and functional impairment.

Definition of Bleed Types

Spontaneous Bleeds: Bleeding for no apparent/known reason particularly into the joints, muscles, and soft tissues.

Traumatic Bleeds: Bleeding event occurring for an apparent/known reason.

Note: Bleeds related to a procedure/surgery such as hematomas/bruising resulting from any surgeries or invasive procedures (eg, tooth extractions, venipuncture, or subcutaneous drug administrations) or invasive diagnostic procedures (eg, lumbar puncture, endoscopy with biopsy) would NOT be counted as bleeds. Bleeds related to procedure/surgery are not associated with any trauma except procedure/surgery-induced trauma.

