Definition of Factor Replacement Regimens

Prophylaxis Therapy: The regularly scheduled and regimented administration of factor replacement therapy to prevent bleeding.

Preventative Therapy: Infusion of clotting factor that is given in anticipation of a planned physical activity that has a high risk of injury (eg, surgery or sporting activity).

On-Demand Therapy: The administration of factor replacement therapy only at the time of an acute bleeding event.

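### Does SAP 3.1 widen the protocol's definition of a treated bleed by accepting an infusion of any type within 72 hours?

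*SAP*

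**What the plan says.** SAP 3.1 names Protocol Appendix 2 as the source of the bleed definition and then gives a rule for classifying each bleed. Two conditions must both hold for a bleed to be treated: the bleeding eDiary or CRF shows it as treated, and the infusion record shows factor within 72 hours of the start of bleeding. The infusion may be of any kind: "regardless of the type of treatment (preventive, prophylaxis or rescue medication), it will be considered as a treated bleed". A second sentence covers the opposite case, opening with "If a bleed is not treated with FIX/FVIII infusion according to the Bleeding eDiary or the Bleeding CRF"; such a bleed is untreated.

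Protocol Appendix 2 defines a treated bleed as "An event necessitating administration of coagulation factor within 72 hours of signs or symptoms of bleeding" and an untreated bleed as "A bleeding event not necessitating administration of coagulation factor within 72 hours of signs or symptoms of bleeding". In a separate block on regimens it defines prophylaxis as "The regularly scheduled and regimented administration of factor replacement therapy to prevent bleeding" and preventative therapy as "Infusion of clotting factor that is given in anticipation of a planned physical activity" carrying a high risk of injury. Only on-demand therapy is tied there to an acute bleed.

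Protocol section 9 lets the SAP modify the protocol, but says that "any major modifications of the primary endpoint definitions or their analyses will also be reflected in a protocol amendment".

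**The concern.** Read side by side, the two definitions seem to use different tests. Appendix 2 turns on need. SAP 3.1 turns on a record plus any infusion in the window, and it lists two kinds of infusion that Appendix 2 defines by purposes other than treating a bleed. Everyone in the study is meant to be on regular prophylaxis, so a scheduled dose will often fall within 72 hours of a bleed by coincidence. The SAP declares no departure from Appendix 2 and does not say that the bleed record stands for need.

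Treated bleeds are the numerator of the SAP's ABR formula. According to Protocol 1.2 the data "will serve as the control for comparison with post gene therapy efficacy". If bleeds that needed no factor entered the treated count, the control rate would be too high and gene therapy would look better against it. A wider definition of the primary endpoint might also have needed a protocol amendment.

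**Working it through.** **Step 1. Put each kind of bleed through both definitions.** The plan states no figure to reproduce, so the main check is textual.

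| Bleed record | Infusions within 72 h of start | SAP 3.1 | Appendix 2 |
|---|---|---|---|
| Not treated | None | Untreated | Untreated |
| Not treated | Routine dose only | Untreated | Untreated, if the record reflects need |
| Treated | Dose given for the bleed | Treated | Treated |
| Treated | Only a dose logged as prophylaxis or preventive | Treated | Treated, if the bleed needed factor |
| Treated | None | Fails the first sentence; not named in the second | Untreated, by implication |

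The second row answers the main worry: a coincidental routine dose does not make a bleed treated. In the fourth row the definitions part only if the participant or site recorded a bleed as treated when it needed no factor. Appendix 2 attaches need to the event and sets no condition on how the infusion is labelled. A bleed handled with a dose logged as prophylaxis therefore meets Appendix 2, and the SAP's any-type wording keeps it in. The last row is settled by Appendix 2, which SAP 3.1 cites.

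**Step 2. How much does the 72-hour check screen out?** Protocol 1.2 gives background dosing frequencies from four times a week to twice a month. These are not this cohort's schedules, which follow each product label and medical need (Protocol 5.3.1). The spacings below are assumed.

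Pass rate = share of onset times for which the next routine dose is at most 3 days away.

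| Schedule | Gaps (days) | Onset unrelated to dosing | Onset only in first half of gap | Onset only in second half of gap |
|---|---|---|---|---|
| 4 a week | 2, 2, 2, 1 | 7/7 = 100% | 100% | 100% |
| 3 a week | 2, 2, 3 | 7/7 = 100% | 100% | 100% |
| 2 a week | 3, 4 | (3 + 3)/7 = 86% | (1.5 + 1)/3.5 = 71% | 3.5/3.5 = 100% |
| Weekly | 7 | 3/7 = 43% | 0% | 3/3.5 = 86% |
| Twice a month | 365.25/24 = 15.2 | 3/15.2 = 20% | 0% | 3/7.61 = 39% |

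At frequent dosing the time check separates little and the bleed record does the work. Passing the check is not enough to be treated, so these rates are not misclassification rates.

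**Step 3. Size, under an assumed error rate.** Let f be the share of SAP-treated bleeds that needed no factor. The documents do not give f. Leaving aside the rule on what counts as a new bleed, ABR under Appendix 2 = (1 − f) × ABR under the SAP, so the SAP figure is higher by 1/(1 − f) − 1:

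- f = 0: 0%
- f = 10%: 1/0.9 − 1 = 11%
- f = 20%: 1/0.8 − 1 = 25%
- f = 30%: 1/0.7 − 1 = 43%

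For one participant, a single reclassified bleed moves ABR by 365.25/182.625 = 2.0 over six months of follow-up, or by 365.25/365.25 = 1.0 over a year. All of this depends on f, which is zero if the bleed record is accurate.

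**Step 4. Direction.** Only new bleeds count. Under Appendix 2 a further treated bleed at the same site is new only if it occurs more than 72 hours after treatment of the first one stopped. Take a bleed treated on demand on day 0, a routine dose on day 2, and a second same-site bleed on day 4, again treated on demand.

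- If routine doses count as treatment, the interval is 4 − 2 = 2 days = 48 hours, and one bleed is counted.
- If they do not, it is 4 − 0 = 4 days = 96 hours, and two are counted.

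The SAP does not say whether its any-type wording reaches this stop time. If it does, it can lower the count, so the any-type rule cannot be said only to raise treated ABR.

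**The case for a change.** The best case for a change is that the link between the bleed record and need is inferred, not written. The bleed fields that Protocol 6.3 lists for the diary are date, time, location and whether the bleed was traumatic or spontaneous; no treated yes/no item appears. This is the primary endpoint, a clarification would take two sentences, and the recorded reason for each infusion would support a second table of treated ABR. ABR of all bleeds is not a perfect safeguard either, because SAP 3.1 counts every untreated occurrence separately while treated bleeds follow the new-bleed rule.

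Part of this stands. The SAP leaves three things unsaid: that the record stands for need, where a bleed recorded as treated with no infusion in the window belongs, and whether routine doses count towards the end of treatment. But SAP 3.1 explicitly relies on a bleeding eDiary or CRF entry on treatment, and the forms themselves are not among the documents, so a short field list does not show that the entry is missing. The first two sentences would only write down what an analyst following SAP 3.1 and Appendix 2 would do. The third point is missing detail with no shown effect.

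The extra table would not be a better estimate. Infusion reason is also a diary entry, nothing shows it to be more accurate than the bleed record, and a reason-coded rule would drop bleeds handled with a dose logged as prophylaxis. Choosing between the rules would depend on how the Phase 3 studies count bleeds, which these documents do not give.

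**Conclusion.** No change to the plan follows. The wording differs, but SAP 3.1 reads as an operational form of Appendix 2: the bleed record carries the element of need, the infusion record confirms timing, and the any-type wording avoids losing bleeds because of how a dose was labelled. The SAP's version history describes this text as an algorithm for defining and counting bleeds, which fits that reading. On that reading there is no major change of definition to put into an amendment.

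The effect on treated ABR cannot be sized or signed from the documents and may be zero. The pass rates of 20% to 100% describe a check that is not sufficient on its own, and the 0% to 43% range rests wholly on an assumed error rate. The consequence here is also limited: the study is descriptive with no hypothesis test (SAP 5.1), and ABR is reported for treated bleeds and for all bleeds (SAP 6.1.1).

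The conclusion assumes that the diary or CRF entry on treatment exists, as SAP 3.1 says, and is completed with reasonable accuracy. Whether the later gene therapy comparison is affected depends on counting rules outside these documents. What remains is a gap in wording that analysts would fill sensibly.
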